#### 9.3.3 Abridged 12 week end of observation questionnaire for GP

For evaluable patients providing consent and for whom a completed baseline questionnaire has been received by the DSRU, at least 13 weeks after starting antiplatelet therapy, their GP will be contacted and invited to complete an abridged "end of observation" SCEM questionnaire. This will gather information on clinical events of medical interest reported since the date of discharge from secondary care up to the end of the 12 week observation period, and recorded within patients medical charts. This may not be required for all patients and will be dependent on the care pathway, as some patients may not be seen again by the specialist. The purpose of sending an abridged questionnaire to the GP is to ensure complete information on the primary outcomes of interest is obtained where possible. Data obtained from this abridged 12 week SCEM questionnaire will include:

- Anticoagulant/antiplatelet treatment regimen which the patient had received
- Event reports of selected risks of interest (Table 3)
- Cause and date of death (if died)
- $\circ$   $\,$  Date and reasons for treatment regimen change (if changed) including switching
- Any newly prescribed concomitant treatments

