#### Part 1: Covariate data

Thirteen weeks post antiplatelet therapy start date, the specialist HCP will be prompted to complete a second questionnaire which will gather information on medical history and medication use prior to or present on start date; changes on general health and medications during treatment and clinical events of medical interest. For some patients, the patient's GP will also be contacted to complete an abridged end of survey questionnaire. This will depend on the care pathway and whether the specialist HCP will have any further contact with the patient after discharge to primary care.

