 $\begin{array}{rcl} ID_t = & \underline{Number \ of \ first \ reports \ of \ an \ event \ during \ treatment \ for \ period \ t \ x \ 1000} \\ & & Number \ of \ patient-weeks \ of \ treatment \ for \ period \ t \end{array} \\ Thus, \ ID_t = & \underline{N_t \ x \ 1000} \\ & & D_t \end{array} \\ where: N_t = & Number \ of \ first \ reports \ of \ an \ event \ during \ treatment \ for \ period \ t, \\ and & D_t = & Number \ of \ patient-days \ of \ treatment \ for \ period \ t \ / \ 7 \end{array}$ 

IDs will also be calculated for each event for all 12 weeks during treatment combined  $(ID_A)$ , and the first week after stopping  $(ID_{SW1})$  if patient stopped (and where patients are recorded as remaining on treatment for at least 1 week) after index date.

Sensitivity analyses will examine any under-reporting by including events of interest recorded in primary care medical charts and confirmed on follow-up for those patients discharged to primary care, during the 12 week observation period.

As IDs for the overall cohort may sometimes mask significant signals in specific risk groups, the subgroups defined by specific characteristics (e.g. previous history of ACS or haemorrhage, previous/concurrent use of selected medications, off-label indication

<sup>1 It should be noted such quantification of rate does not only reflect the rate attributable to the drug but also reflects the background rate in the general population and rate attributable to other factors such as age or other disease risk factors

<sup>2 Ideally, the exposure time would be censored at the time of the first event. However, since there are a large number of health outcomes of interest and the censoring would be different for each outcome, the denominator for the crude ID will not initially include censoring. If an elevated crude ID is identified in this monitoring analysis, a subsequent analysis with appropriately censored denominator will be performed for that outcome.

groups, rivaroxaban naïve or past user) will have IDs calculated and compared according to strata for relevant events, where appropriate.

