4. Each patients' GP will be contacted to obtain information on key study variables – this supplementary information will contribute to identification of relevant cases, where information may be missing from questionnaires completed by specialists

Specific methods to handle issues of missing or conflicting data, will be summarised within the detailed study specific Data Management Plan (DMP) which will be constructed to assist database development and data analysis. In brief, the missingness pattern of primary covariates and proportions thereof in the study subjects will be presented to explore plausibility of missing at random (MAR) assumption to justify subsequent regression analysis. Multiple imputation is planned. However, we will compare the results of this to a complete case analysis. If the two are substantially different we will evaluate what the reasons may be. Thus, imputation will be performed using STATA SE 12 ICE imputation for exposure variables with less than 20% missing data and a sensitivity analysis conducted to determine magnitude and direction of bias arising from missing data from complete case analysis as relevant to Section 8.2 primary and secondary objectives.

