- $\circ$   $\,$  Confounding by severity is possible and needs to be accounted for.
- Under- and mis- reporting of outcomes is possible; specialist HCPs' notes may be incomplete with regard to medical history and non-cardiovascular related outcomes of interest associated with current treatment. The two-phase data capture approach could facilitate compliance with data reporting as well as spreading workload for specialist HCPs. By obtaining information from all patients GPs and access to primary medical charts, under ascertainment of outcomes can be minimised. In contrast, over-recording of health related events in the period following the administration of the baseline questionnaire are possible due to increased specialist HCP attention to special populations of interest (patients with concomitant complications) as detailed in the questionnaire, however since information is being abstracted from medical charts such bias is unlikely. However, this is likely to be similar in the contextual cohort.
- Regarding the definition of bleeding, in this study case definitions are based on acceptable agreed clinical standards and aim to address specific regulatory questions in the context of the risk management plan for the product.
- Immortal time bias is possible arising from misclassification of exposure to the study drug.
- With this patient population, patient attrition and loss to follow-up may introduce selection bias, however, the relatively short period of observation should mitigate this possibility at least to some extent.
- Misclassification bias will be minimised by well defined outcome and follow-up of medically important events. Patients with selected events of interest will be followed-up with regard to co-prescribed medicines and concurrent illness. Events that represent features of the respective indications will be taken into account when safety signals are investigated (i.e. confounding by indication).
- Furthermore unidentified poor adherence may also lead to misclassification of exposure. However, as with many observational studies, the degree of patient compliance in taking the prescribed medication cannot be ascertained. Whilst it is not possible to be sure the patient used the medication, it is almost certain that the patient received it since starting treatment is required for study participation. This is unlikely to be significant in this patient population, and for the 12 week period of observation.

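### The protocol promises that every patient's GP is contacted, but its procedures send the GP form only to some, so major bleeds recorded outside the specialist chart can be missed

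*Protocol*

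**What the plan says.** Two rules for contacting the GP stand in the current text.

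**Every patient.** Section 9.7.6 lists among its measures against missing data: "Each patients' GP will be contacted to obtain information on key study variables". Section 9.9 builds on it: "By obtaining information from all patients GPs and access to primary medical charts, under ascertainment of outcomes can be minimised". Section 9.1 also states the GP contact without restriction, and so does the opening of 9.3.3 for evaluable patients with a completed baseline questionnaire.

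**Some patients.** Further on in 9.3.3, about the same questionnaire: "This may not be required for all patients and will be dependent on the care pathway". Section 9.4.2, Part 1, says: "For some patients, the patient's GP will also be contacted to complete an abridged end of survey questionnaire". The only criterion follows there: "This will depend on the care pathway and whether the specialist HCP will have any further contact with the patient after discharge to primary care".

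Section 9.3.3 gives the purpose of the form as complete information on the primary outcomes. Section 9.1 expects care to be shared with primary care for most patients.

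On the use of GP data, 9.7.1 has primary events adjudicated on all available information from the study questionnaires, follow-up and other documents. Section 9.7.4, which covers the other bleeding outcomes, says: "Sensitivity analyses will examine any under-reporting by including events of interest recorded in primary care medical charts".

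**The concern.** Sites and the coordinating centre cannot follow both rules, and the limitations section claims a safeguard that the procedures do not deliver.

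The gap touches the primary outcome. Section 9.9 concedes that specialist notes may be incomplete for non-cardiovascular outcomes. Gastrointestinal and urogenital bleeds are outcomes of that kind. A patient still under the specialist may have such a bleed treated elsewhere, with the record reaching only the GP. If the care-pathway rule skips that patient's GP, the event is not counted. Missing events push the estimated incidence down, which is the unfavourable direction for a study set up to quantify bleeding risk. With so few expected events, one or two missed bleeds change the result visibly.

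**Working it through.** **Inputs (9.5 and 9.7.1).** Expected 12-week risk of primary major bleeding 0.5%, made up of intracranial 0.1%, gastrointestinal 0.3% and urogenital 0.1%; precision ±0.4%; 95% confidence; 1193 patients per cohort; at least five reports needed for hazard modelling.

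**1. The plan's own figure.** n = z²p(1−p)/d² = 1.96² × 0.005 × 0.995 / 0.004² ≈ 1194.5. A finite population correction with an assumed population of 1,000,000 gives 1193.03, and the same correction reproduces the other Table 4 cells tried. The 1193 stands and is not affected by this point.

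**2. Expected events.** 1193 × 0.005 = 5.97 per cohort. Gastrointestinal and urogenital sites account for 0.4 of the 0.5 points: 1193 × 0.004 = 4.8 events.

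**3. Effect of each missed bleed.** 1/1193 = 0.084 percentage points, about one sixth of 0.5%. Six events give 6/1193 = 0.50%. Four give 4/1193 = 0.34%, which is also below the five-report minimum for hazard modelling.

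**4. Illustration over assumed ranges.** Let g be the share of patients without a GP form and s the share of their primary bleeds absent from the specialist chart. Assume that bleeding risk is the same with and without a GP form. Then the observed risk is 0.5% × (1 − g × s). The document gives neither g nor s.

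| g | s | Observed risk | Expected events | P(at least 5 events) |
|---|---|---|---|---|
| 0 | – | 0.50% | 5.97 | 0.71 |
| 0.25 | 0.25 | 0.47% | 5.6 | 0.66 |
| 0.50 | 0.50 | 0.375% | 4.5 | 0.46 |
| 0.75 | 0.75 | 0.22% | 2.6 | 0.12 |

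The probabilities are exact binomial with n = 1193. The table shows how sensitive the result is; it does not predict the bias.

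**5. Do the planned sensitivity analyses cover the gap?** Those using GP or primary care data are in 9.7.3 and 9.7.4, for the secondary and exploratory objectives. They cannot recover an event where no GP was asked. The sensitivity analyses named in 9.7.1 concern immortal time and adjudication, not GP ascertainment.

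**The case against.** The strongest reply is that the care-pathway rule probably works in the right direction. Sections 9.3.3 and 9.4.2 tie the form to whether the specialist will see the patient again, so its natural reading sends the form to patients last seen at discharge and skips those still followed in hospital. The specialist form covers events charted over 13 weeks (9.3.2). Charts from other specialities may be examined (9.1.1), and study staff may access primary and secondary care charts (10.3). Primary events are severe (Table 1), so many should reach the hospital record.

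Most of this stands, and it limits the loss. It does not remove it: 9.9 itself says that specialist notes may be incomplete for non-cardiovascular outcomes, and its remedy is the GPs of all patients. The criterion is also not operational, since neither its direction nor a cut-off is stated.

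A reader might infer three stronger points that the document does not support.

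- *Patients last seen at discharge are counted as event-free for the full 12 weeks.* Section 9.7.1 ends a non-case's time at exit, loss to follow-up or treatment stop plus 2 days. Exit date is undefined, and 9.2.5 does not say how a patient with only a specialist form is handled. Full counting is possible, but it is an inference.
- *The main analysis in 9.7.4 leaves out post-discharge events by rule.* Post-discharge events in the specialist chart are covered by the 13-week form. The sensitivity analysis concerns events in primary care charts confirmed on follow-up. The text does not say that GP-form events are excluded from the main analysis; it is unclear.
- *The cohorts are compared on biased figures.* The primary analysis is run separately in each cohort, and the ENCePP checklist (Annex 2) states that no formal hypotheses are tested. Unequal ascertainment would affect the contextual reading, not a test.

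**Conclusion.** The contradiction is real, lies in current text, and concerns the safeguard for the primary outcome. Its direction is clear: where GPs are not asked, the primary incidence can only lose events. Each lost bleed costs about 0.08 percentage points out of an expected 0.5%. That is small beside the ±0.4% half-width, but it is a systematic error that the confidence interval does not reflect. The total size is unknown, and any figure depends on assumed values of g and s.

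This should be fixed, but it does not invalidate the design. The wording conflict and the downward direction are certain. How many events are at risk is not, because the pathway rule most plausibly covers the patients in whom the loss would be greatest.

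**What to change.** 1. **Sections 9.3.3 and 9.4.2.** Send the GP form for every evaluable patient in both cohorts, in line with 9.1, 9.7.6 and 9.9, and delete the care-pathway exception.
2. **Section 9.7.4.** State that confirmed GP-recorded events count in the main analysis, as 9.7.1 already implies for the primary outcome, and make the specialist-only count the sensitivity analysis.
3. **Section 9.7.1.** Add a sensitivity analysis of the primary outcome for patients whose GP form is not returned; 9.3.5 expects some non-response. Options are to restrict it to patients with a GP form, or to censor at the last documented contact.

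Censoring at the last specialist contact should not become the main rule, because that contact may itself be triggered by a bleed. Suppose 30% of patients were covered for only 1 of 12 weeks, yet the specialist chart captured every major bleed. Person-time would fall to 1 − 0.3 × 11/12 = 72.5%, and the rate would be inflated by 1/0.725 − 1 = 38%. These inputs are assumptions, chosen to show that the bias can also run upward.

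The cost is some additional GP questionnaires, already promised elsewhere in the protocol, and a few sentences of analysis text. The sample size stays at 1193 per cohort.

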Study start is defined as the date that the first patient is recruited into the study (18th September 2015), and continue for a maximum of 36 months, or until the target sample size (1193 tbc) for both cohorts has been achieved (whichever is the soonest). The final cohort sizes, period of observation and the duration of the SCEM study will be dependent on the level of prescribing of rivaroxaban in combination with standard oral antiplatelet therapy by specialist HCPs in England and Wales. Data collected during later calendar time periods can be compared with earlier periods to identify any trends that may emerge. Slow uptake may impact on the ability to meet the study objectives; in this instance, further discussions with the regulatory authorities regarding study feasibility will be needed.

Patients will be observed from the date antiplatelet therapy was prescribed as part of the acute management of the ACS in both the rivaroxaban group and the contextual Version 7 Date: 30/08/2017

cohort for 13 weeks in order to allow for detection of outcomes associated with treatment initiation (this will allow for a delay between antiplatelet therapy administration as part of the acute treatment for the ACS, and the subsequent start of rivaroxaban to ensure 12 complete weeks of observation time for analysis). The index date for analysis for both groups will be defined dependent on the prescribing patterns observed in real life use. Since patient care is likely to be shared between secondary and primary care for most patients during the observation period, the patient's GP will be contacted at least 13 weeks after antiplatelet therapy start date to complete an abridged questionnaire to collect any information on outcomes of interest that they are aware of during the observation period to minimise under-reporting on selected outcomes. For the main statistical analysis, events will be censored at 12 weeks post index date, should they be reported after this time period. However, events of interest will be included and detailed in study reports even if they occurred after the 12 week time period. Where additional outcomes are identified that have not be reported by the initiating prescriber, these will be followed-up with the GP to ascertain further information.

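### The protocol gives conflicting rules on who is sent the GP outcome form; if the conditional rule is applied, the stated safeguard against missed bleeds fails for patients kept under the specialist.

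*Protocol*

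**What the plan says.** The protocol states two rules for the abridged 12-week GP questionnaire.

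**Every patient**
- Section 9.7.6 (Missingness), in its list of steps against missing data: "Each patients' GP will be contacted to obtain information on key study variables".
- Section 9.9 (Limitations): "By obtaining information from all patients GPs and access to primary medical charts, under ascertainment of outcomes can be minimised".
- Section 9.1 (Study Design) sets no care-pathway condition. The GP is contacted at least 13 weeks after antiplatelet therapy starts "to complete an abridged questionnaire to collect any information on outcomes of interest that they are aware of during the observation period to minimise under-reporting".
- The opening sentence of section 9.3.3 is also unrestricted. It covers evaluable, consented patients with a completed baseline questionnaire.

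**Some patients**
- Section 9.3.3 then continues: "This may not be required for all patients and will be dependent on the care pathway".
- Section 9.4.2, Part 1 says that for some patients the GP "will also be contacted to complete an abridged end of survey questionnaire", depending on the care pathway and on whether the specialist will see the patient again after discharge.

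Section 9.3.3 gives the purpose of the form as complete information on the primary outcomes. Section 9.9 says why a second source is wanted: specialists' "notes may be incomplete with regard to medical history and non-cardiovascular related outcomes of interest". The primary outcome (8.2, Table 1, 9.7.1) is TIMI major bleeding not related to CABG, at intracranial, gastrointestinal and urogenital sites.

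**The concern.** The two rules cannot both be operated, and 9.3.3 conflicts with itself. The conflict concerns how primary events are found, so it is more than a drafting slip.

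Under the conditional rule, the patients most likely to have no GP form are those the specialist continues to see. Section 9.2.2 confirms that such patients exist, since some may be managed in secondary care alone. For them, ascertainment rests on the specialist's record, which is the source 9.9 says may be incomplete for outcomes of this kind. The mitigation claimed in 9.9 would then not be what the study does.

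The planned checks would not reveal the gap. The under-reporting sensitivity analysis in 9.7.4 adds primary-care events only for patients discharged to primary care. The one in 9.7.3 uses GP data, which these patients would not have. The sensitivity analyses listed in 9.7.1 for the primary outcome do not address this source of loss.

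The primary objective is an absolute incidence within each cohort, so missed events lower the estimate directly, whether or not the cohorts differ.

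**Working it through.** **1. The plan's own figure.** Section 9.5 gives 1193 patients per cohort to estimate 0.5% within ±0.4 percentage points. The normal-approximation formula is n = 1.96² × p(1 − p)/d². With p = 0.005 and d = 0.004 it gives 1194.5. A finite-population correction for 1,000,000 gives 1193.0, so the figure reproduces.

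**2. Expected events.** 1193 × 0.005 = 5.97 per cohort. Section 9.7.1 requires at least five reports of an event before modelling its hazard. From the binomial distribution, P(at least 5) = 0.71 with complete ascertainment.

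**3. Share of the primary outcome at stake.** Section 9.5 splits the 0.5% into 0.1% intracranial, 0.3% gastrointestinal and 0.1% urogenital. Gastrointestinal plus urogenital is 0.4/0.5 = 0.8. Intracranial bleeds are taken here as always captured by the specialist, which is an assumption.

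**4. Loss under the conditional rule.** The documents give neither the share of patients without a GP form (s) nor the proportion of these bleeds captured in specialist records (c). Assumed ranges are s = 30% to 50% and c = 90% to 70%.

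Fraction of primary events missed = 0.8 × (1 − c) × s

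| c | s | Fraction missed | Events missed of 5.97 | Observed incidence | P(at least 5) |
|---|---|---|---|---|---|
| 90% | 30% | 0.8 × 0.1 × 0.3 = 2.4% | 0.14 | 0.488% | 0.69 |
| 70% | 50% | 0.8 × 0.3 × 0.5 = 12% | 0.72 | 0.440% | 0.60 |

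For a given c and s, this is an upper bound on what a universal GP form would recover. It assumes that every form is returned and that each one finds every missed event. Section 9.3.5 itself expects some specialists and GPs not to respond.

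**5. How far the answer depends on the assumptions.** If incompleteness is applied to all three sites, observed incidence = 0.5% × (1 − s + s × c):
- s = 10%, c = 90%: 0.495%, 5.9 events, P(at least 5) = 0.70.
- s = 25%, c = 75%: 0.469%, 5.6 events, P = 0.66.
- s = 50%, c = 50%: 0.375%, 4.5 events, P = 0.46.

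The effect therefore runs from negligible to an expected count below the protocol's five-report threshold. The documents do not say where in that range the study lies.

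**The case against.** **The omitted group may be where a GP form adds least.** Patients still seen by the specialist have the full 12-week specialist questionnaire (9.3.2), with targeted questions on major bleeds (Table 3). TIMI major bleeds are severe, so many should reach a hospital record. Consent covers primary and secondary care charts (9.1, 10.3), charts from other specialities may be examined for selected outcomes (9.1.1), and all reported deaths are followed up (9.3.4). This stands as a reason to expect capture towards the upper end of the assumed range. It does not supply a systematic second source: chart review elsewhere is optional, and follow-up starts only once an event has been reported.

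**The group may be small.** Section 9.1 expects care to be shared with primary care for most patients. This also stands, and it makes large specialist-only shares hard to defend.

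**The loss is small by the study's own yardstick.** A fall from 0.5% to between 0.488% and 0.44% is well inside ±0.4 percentage points. That is correct and limits the severity.

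**A stronger reading is tempting.** A reader might infer that the conditional rule biases the contrast between cohorts, on the idea that patients given a new add-on drug stay under specialist review more often. The documents do not support this. They give no care-pathway shares by cohort and no statement that follow-up differs, and 9.7.1 runs the primary analysis separately in each cohort. Any ratio built on unequal shares would rest on invented inputs. A reader might also take 9.9 to say that specialist notes are incomplete; it says only that they may be.

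**Conclusion.** The contradiction is real and needs correcting. Sections 9.3.3 and 9.4.2 make the GP form conditional, while 9.7.6 and 9.9 say every GP is contacted. The unrestricted wording in 9.1 and at the start of 9.3.3 agrees with the latter.

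The consequence depends on which rule is operated. If every GP is contacted, only the wording is at fault. If the conditional rule is applied, the safeguard in 9.9 does not exist for patients kept under the specialist, and primary incidence may be somewhat understated. On the assumed ranges, about 2% to 12% of roughly 6 events per cohort would be missed, or 0.14 to 0.72 of an event. That is small against the planned precision, but with so few expected events one or two missed bleeds would be visible in the result. The true size cannot be determined from the protocol. Different ascertainment in the two cohorts is a possibility to monitor, not a finding.

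The correction is worth making because the rule governs ascertainment of the primary outcome and the remedy is cheap.

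**What to change.** - Amend 9.3.3 and 9.4.2 to match 9.7.6 and 9.9: send the abridged GP form for every consented patient with a completed baseline questionnaire, in both cohorts, whatever the care pathway.
- Define the form's time window for patients not discharged. At present 9.3.3 starts it at discharge from secondary care, which leaves it undefined for them. For these patients, have it run from the index date to the end of the 12-week observation period.
- Extend the under-reporting sensitivity analysis in 9.7.4 to all patients with a GP form, instead of only those discharged to primary care.
- Report GP return rates by cohort, so that any difference in ascertainment can be seen.

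If the sponsor keeps the conditional rule instead, 9.7.6 and 9.9 must be corrected and the all-GP mitigation withdrawn.

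**Cost.** Protocol wording, plus more GP mailings and reminders. Consent already covers GP charts, and a reminder process exists (9.3.5). Recruitment began in September 2015 and this version is dated August 2017, so any patients already enrolled without a GP form would need retrospective mailing.
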